***Female partner exclusion criteria***

- 1. Unwillingness of the partner to make the required attempts at sexual intercourse during the screening period (4 requested sexual intercourse attempts) and during the 4-weekly assessment periods (4 requested sexual intercourse attempts per period) in the treatment phase.
- 2. Unwilling to disclose any experienced adverse events to the site study team.
- 3. Partner cannot communicate reliably with the Investigator
- 4. Any other condition that would prevent the patient from completing the study, as judged by the Investigator

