### **Secondary Objectives:**

To investigate the following in patients after nerve sparing prostatectomy treated with MED3000 for 12 weeks:

1. The efficacy of MED3000 in patients at weeks 4, 8 and 12 using:
  - a. The change from baseline in Self-Esteem and Relationship (SEAR) questionnaire for men
  - b. The change from baseline in Urinary incontinence using the Expanded Prostate Cancer Index Composite (EPIC) - (climacturia question added to EPIC)
  - c. Change from baseline in all domains of the IIEF.
2. The change from baseline in 24 hour pad weight and usage number per day at 12 weeks.
3. The change from baseline of the stretched flaccid penile length following 12-weeks of treatment
4. Treatment-related adverse events in male patients and female partners occurring during treatment with MED3000.

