##### ***Male subject inclusion criteria***

1. Men who underwent bilateral nerve-sparing radical prostatectomy between 18 and 48 months prior to study commencement
2. Age 40 – 70 at the time of screening.
3. Diagnosed with prostate cancer:
  - a. PSA < 20 ng/ml
  - b. Gleason score <= 8
  - c. PCa stage <= T3a
4. Normal pre-radical prostatectomy erectile function (EPIC-CP question 8 score of 0 [firm enough for intercourse] or IIEF > 26)
5. Baseline erectile dysfunction at time of screening (despite use of erectogenic aids of any kind) and at enrolment following washout (IIEF-EF domain <= 25)
6. Sexually active, in a stable heterosexual relationship for at least 6 months prior to screening
7. Female partner meets their respective inclusion and exclusion criteria
8. Able to understand and complete patient questionnaires
9. Serum PSA undetectable (no evidence of disease recurrence)
10. Willing and able to provide written consent to participate in the study (note: both the patient and his female partner must provide written consent to participate before any study related procedure is undertaken)
11. Willing to refrain from the use of other erectogenic devices and pharmaceutical interventions during the washout and 12-week treatment periods.

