##### ***Male subject exclusion criteria***

1. Anatomical abnormalities in the genitalia or pelvic region such as severe phimosis
2. Post-RP complications that could impact safety or effectiveness of medical therapy for

- erectile function (urinary or intestinal fistula, unresolved anastomotic leak)
- 3. Tumor upstaging beyond T3a
- 4. Incomplete / sub-total nerve sparing on either side
- 5. Previous or scheduled treatment with pelvic salvage radiotherapy and/or androgen deprivation therapy
- 6. Prior receipt of androgen deprivation therapy
- 7. Unwillingness of the patient to make the required attempts at sexual intercourse during the screening period (at least 2 sexual intercourse attempts) and during the 4-weekly assessment periods (at least 4 sexual intercourse attempts per period) in the treatment phase.
- 8. Patient cannot communicate reliably with the Investigator
- 9. Any significant or serious cardiovascular, pulmonary, hepatic, renal, gastrointestinal, hematological, endocrinological, metabolic, neurological or psychiatric disease which, in the opinion of the Principal Investigator, renders the male patient unfit to take part in the investigation
- 10. Patient has any history of an unstable medical or psychiatric condition or using any medication that, in the opinion of the PI, is likely to affect the patient's ability to complete the investigation or precludes the patient's participation in the investigation
- 11. Hypersensitivity to any of the excipients
- 12. Any clinically significant abnormal laboratory, vital signs or other safety findings as determined by medical history, physical examination or other evaluations conducted at screening or on admission
- 13. History of severe uncontrolled diabetes
- 14. Patients with nursing partners, known pregnant partners or partners who wish to become pregnant
- 15. Clinical evidence of alcohol or drug abuse (including marijuana) (in last 12 months)
- 16. Patients receiving testosterone pellets
- 17. History of hypogonadism
- 18. Prior surgical or intralesional treatment for Peyronie's disease
- 19. Any other condition that would prevent the patient from completing the study, as judged by the Investigator

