***Female partner inclusion criteria***

- 1. Willing and able to provide written consent to participate in the study (note: both the patient and his female partner must provide written consent to participate before any study related procedure is undertaken)
- 2. Documented written informed consent

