site at Visit 5 Adverse events. Protocol compliance will be assessed by questioning the patient about their use of MED3000 and the number of unused tubes of MED3000 available. Patients will be asked about any changes to their concomitant medication and any new or changes to AEs (including their partner). Additionally, patients will be asked whether the patient or partner predominantly applied the gel to the glans penis prior to sexual intercourse.

Visit 4 (phone -Week 8 ( $\pm$  1 week)): Patients will be asked to complete the IIEF, EPIC, climacturia and SEAR questionnaires. The patient will bring the completed questionnaires to the site at Visit 5. Protocol compliance will be assessed by questioning the patient about their use of MED3000 and the number of unused tubes of MED3000 available. Patients will be asked about any changes to their concomitant medication and any new or changes to AEs (including their partner). Additionally, patients will be asked whether the patient or partner predominantly applied the gel to the glans penis prior to sexual intercourse.

Visit 5 (on-site -Week 12 ( $\pm$  1 week)): Patients have PSA serum samples taken and have a genital examination. Patients will also complete the IIEF, EPIC, climacturia and SEAR questionnaires. An assessment of the stretched flaccid penile length will be performed, heart rate and blood pressure will be measured. AEs, changes in concomitant treatment, and protocol compliance and a genital assessment will be assessed. The patient will return all used MED3000 tubes and unused MED3000 treatment at this visit and full verification of MED3000 usage compliance determined. The site will also perform an assessment of the patient's 24 hour pad weight and the number of pads used. Additionally, patients will be asked whether the patient or partner predominantly applied the gel to the glans penis prior to sexual intercourse.

Follow-up Visit 6 (phone-7 day post-study treatment, ( $\pm$  2 days)): Patients will provide details about ongoing or new adverse events and any new concomitant treatment. Usage of erectogenic aids will also be recorded. Patient will be instructed to continue with his primary urologist for PSA monitoring per standard of care.

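### Hypersensitivity to the gel's excipients is a named exclusion for the man only; for the exposed female partner it is left to a discretionary catch-all that prompts no allergy question

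*Combined protocol and SAP*

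**What the plan says.** Section 4 (Subject Selection) has separate eligibility lists for the man and his partner, joined by male inclusion 7: "Female partner meets their respective inclusion and exclusion criteria".

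- **Man.** Exclusion 11 is "Hypersensitivity to any of the excipients". Exclusion 14 covers partners who are nursing, known to be pregnant or hoping to conceive; it is the only exclusion in his list about the partner's own condition. Exclusion 19 is a general catch-all.
- **Partner, inclusion.** Both items concern consent; the second reads "Documented written informed consent".
- **Partner, exclusion.** There are four items: unwillingness to make the requested attempts; "Unwilling to disclose any experienced adverse events to the site study team"; "Partner cannot communicate reliably with the Investigator"; and "Any other condition that would prevent the patient from completing the study, as judged by the Investigator".

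On exposure, Section 1 says that either partner may administer the gel. The training summary below Table 1 puts application directly before intercourse. In the Study Visits text for Visits 3 to 5, "patients will be asked whether the patient or partner predominantly applied the gel". Secondary objective 4 in Section 2 is "Treatment-related adverse events in male patients and female partners occurring during treatment with MED3000". Table 1 lists the ingredients.

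**The concern.** The protocol names one risk that can be screened for, and controls it for one of the two people exposed. The partner signs her own consent form, has her eligibility assessed, and has her treatment-related adverse events studied as an objective. Nothing in her own list asks whether she is known to react to an ingredient of the gel.

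The main stake is participant safety: a reaction in a partner with a known allergy would be foreseeable and avoidable. There is a smaller consequence for the data. If the couple stopped using the gel, the man's treatment course would be cut short in a single-arm study of about 20 patients.

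**Working it through.** The plan states no figure on this point, so the check sets the sections side by side and adds a simple exposure count.

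**1. Is there an allergy criterion for the partner?** Hypersensitivity appears once in the eligibility lists, as male exclusion 11. Both female inclusion items concern consent. Female exclusions 1 to 3 concern willingness, disclosure and communication. Male inclusion 7 refers back to the female list and so adds nothing on allergy. Male exclusion 14 deals with nursing and pregnancy only. That leaves female exclusion 4.

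**2. What does female exclusion 4 do?** It turns on whether the patient, meaning the man, can complete the study. A partner's allergy could fall under it indirectly, because he cannot complete without repeated intercourse with her. Its use depends on the investigator's judgement and on the allergy being volunteered. Male exclusion 19 is worded identically, yet the man also has the specific exclusion 11. For him, then, the catch-all was not relied on alone.

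**3. Is she exposed, and how often?**

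| Quantity | Source | Arithmetic | Result |
|---|---|---|---|
| Instructed minimum attempts | Section 3, Intervention | 4 per period × 3 periods | 12 |
| Assumed maximum attempts | Device traceability | 12 per period × 3 periods | 36 |
| Tubes dispensed | Device traceability | 9 cartons × 4 tubes | 36 |

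The instructed minimum is 12 attempts over the treatment period. The figure of 36 is the supply ceiling, not an expected number, and a partner who reacted and stopped would not reach it.

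**4. What happens to the data if a couple stops?** Footnote 7 of the Schedule of Assessments provides Visit 5 assessments, which include the IIEF, for patients who leave the treatment period early. The man would then have an end-of-treatment IIEF, but possibly before Week 12. The per-protocol set in Section 9 requires completion of all sessions up to the 12-week visit, so he would drop out of it. With about 20 patients, one man is 1/20 = 5%.

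**5. Can the criterion be checked within the existing schedule?** Yes. The Schedule of Assessments marks eligibility of both the man and the woman at Visit 1, and the Study Visits text has her attend in person.

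**The case against.** The strongest reply is that female exclusion 4 already covers the case. It stands in her own list, and its natural reading is a condition of hers that would stop the man completing. Once it is applied, male inclusion 7 makes him ineligible. This stands in part. A reader might infer that a partner with a known allergy passes every written criterion, and the documents do not support that: the investigator may exclude her. They also do not require it or prompt the question.

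A second reply is that the risk looks low. The protocol calls the ingredients usual for topical products, describes earlier adverse events as rare and mild, and reports a nonsignificant-risk determination by the FDA. That is fair as to general risk. It does not address someone with a known allergy, and the same argument would make male exclusion 11 unnecessary.

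Third, she is informed before consenting and may attend the training, and her consent form may carry a warning. The consent pages are not available for review, so this cannot be checked. A warning would lower the chance that an allergic partner is enrolled, but it would not be an eligibility criterion.

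Finally, counting a partner's reaction as treatment-related is no flaw in the analysis, since recording such events is the purpose of objective 4. That is correct, and the point does not rest on it.

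**Conclusion.** The point holds as an inconsistency between the two eligibility lists. A named exclusion protects the man; for the partner, who is also exposed, the same risk is left to discretion under a criterion written around his completing the study. It is worth correcting because it concerns the safety of a consented participant and is cheap to change. It does not affect the primary endpoint definition, the statistical tests or the basis for the sample size.

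Two stronger readings should be resisted:

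- **A probability of enrolling an allergic partner.** The documents give no prevalence, so any such figure would rest wholly on an outside assumption.
- **Loss of the man's outcome.** Footnote 7 provides for an end-of-treatment assessment. The supportable consequence is a possibly early assessment and removal from the per-protocol set, at 5% of about 20 patients per affected couple. This assumes that he stops treatment without also withdrawing from the study, after which Section 10 (Withdrawal Criteria) says nothing new is collected.

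The conclusion otherwise rests only on the eligibility lists and on the protocol's own account of her exposure.

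**What to change.** Reconcile the female partner exclusion list with male exclusion 11 and with the exposure that the protocol describes. Add the trial's existing criterion, "Hypersensitivity to any of the excipients", to the partner's list with a reference to Table 1, and check it at Visit 1. Keep female exclusion 4 as the general catch-all.

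The cost is one added eligibility line, one question to a partner who already attends Visit 1, and possibly an occasional couple screened out. No new visit, procedure or analysis is needed.

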## 5. Subject Enrollment

Patients will be recruited through the active patient cohort of the Brigham and Women's urologic men's health clinic and Massachusetts General Hospital. Approximately 20 patients will enter the treatment phase of this study.

The recruitment of patients will primarily be undertaken by research assistant(s) and/or Investigator(s) through the men's health clinic patient cohort, with a research assistant and/or investigator available to support any eligible and interested patients. Patients will initially be approached by his/her healthcare provider who is known to the potential patient and has first-hand knowledge of the patient's medical history. The healthcare provider may be one of the investigators. We will mitigate the possibility of undue influence when subjects are enrolled from among the Investigators' own patients. We plan to employ the following approaches as appropriate separately or in combination:

- Contact the patient in writing initially (via Research Invitation) and allow a patient to make the first contact if they're interested
- Ask a physician colleague, research nurse, or clinical research coordinator to initially explain the study or to re-contact the potential subject after the Investigator has presented the study at a routine in-person or telehealth visit
- Offer patients the opportunity to take home the Consent Form, and call or message back if they wish to participate

We will also review operative records at Brigham and Women's Hospital, and Faulkner Hospital for those patients who have undergone radical prostatectomy surgery during the enrolment period. These patients may not have recently seen a Brigham-affiliated clinician. We will access the operative reports and patient medical records through the electronic medical record. We will screen the medical records for relevant enrolment and exclusion criteria such as nerve sparing status, pathology for stage and margin status, PSA status, presence of erectile dysfunction. If patients are deemed to be potential subjects and have not opted out of receiving research invitations, we will send either a targeted research announcement or personalized research announcement to advise them of the study. If the patient is not enrolled in Patient Gateway we may mail the personalized research announcement. If we have not heard back from the patient after a week we will call them. If patients respond favorably they will complete pre-screening over the phone.

Once the provider gives approval to the research team to continue with contacting the patient, with the patient's verbal permission, during the course of providing medical care, the research assistant or investigator will be introduced to the patient and will be available to support any eligible and interested patients. The subjects will not be paid for their participation in the study. The consenting procedure for the trial will be administered by the members of the investigator site study team.

Mass General Brigham Institutional Review Board  
Intervention/Interaction Detailed Protocol

---

The female partner of the patient will accompany the male patient to his appointment and be informed about the study and asked to participate at the initial visit. The female partner will review and sign her own version of the informed consent form. Both patient and partner must sign their respective informed consent forms before any study related procedure is carried out on either party.

It is not anticipated that advertising will be needed to recruit patients and their partners. Instead, other clinics within Brigham and Women's Hospital/Dana Farber Cancer Institute may cross-refer any suitable patients as necessary.

All potential patients will have the medication risks and possible benefits explained to them and given sufficient time to ask questions and consider whether they wish to participate. Only patients and female partners who have signed the IRB approved informed consent forms may be enrolled into the study.

Non-English speakers, children and those lacking capacity will not be offered participation in the study. Following the Partners Human Research Committee (PHRC) policy on Obtaining and Documenting Informed Consent of Subjects who do not Speak English, non-English speaking patients will not be recruited as a full-translation consent is not available.

Patients will be allowed to withdraw consent at any time without compromising their future clinical care.

Most patients with post-radical prostatectomy erectile dysfunction treated at Brigham and Women's Hospital/Dana Farber Cancer Institute are internally referred to PI or sub-investigator for management. Thus, recruitment from the patient cohort treated by PI or sub-investigator reflects the general population of post-prostatectomy men treated at the institution. Trial information will be disseminated to medical oncology, radiation oncology, and urologic oncology at / Brigham and Women's Hospital / Dana Farber Cancer Institute/ Massachusetts General Hospital. Before patients are approached by the investigation site staff regarding study participation, a health care provider, usually a physician, known to the potential subject and has first-hand knowledge of the patient's medical history will (1) give approval for his/her patient to be contacted for research purposes, (2) initially introduce the study to the patient and (3) obtain the patient's permission to be contacted by study staff. The healthcare provider can introduce the study and obtain the patient's permission to be contacted by study staff verbally during the course of providing medical care.

Data on patient enrolment including race and ethnicity and plan to perform sub-group analyses for efficacy will be recorded. The investigation site staff will reach out to providers in medical oncology, radiation oncology, and urologic oncology to inform them of the study and encourage them to contact research group with potential research subjects, irrespective of whether the patient is met in clinic or via telehealth visit by the primary health care provider. It is planned that visits performed during the study will be via Telehealth, thus limiting the burden of travel for in-person visits.

## 6. STUDY PROCEDURES

Patients will be screened by the research assistant and/or investigator according to the specific inclusion/exclusion criteria.

### ***Schedule of Assessments (Core Investigation)***

	Screening (5 or 4 weeks before Day 1) 	Treatment Period (12 Weeks)				Follow-up Visit
	Visit 1	Visit 2 (Day 1)	Visit 3  (Week 4 ± 1 week)	Visit 4  (Week 8 ± 1 week)	Visit 5  (Week 12 ±1 week)	Visit 6  (Week 13 ±1 week)
Eligibility assessment of male & female	X	X 				
Informed consent (male and female) 	X					
PSA Serum 	X					

Mass General Brigham Institutional Review Board  
Intervention/Interaction Detailed Protocol

	Screening (5 or 4 weeks before Day 1) 	Treatment Period (12 Weeks)			Follow-up Visit
Hormonal assays (testosterone) 	X				
Genital examination	X				X
BMI	X				
IIEF	X	X 	X	X	X
EPIC + climacturia	X	X	X	X	X
SEAR	X	X 	X	X	X
Heart rate and blood pressure	X	X			X
Penile length measurement	X				X
24 hour pad weight and number of pads used	X				X
Treatment		←	→		
MED3000 dispensing		X 			
Adverse events reporting (including device deficiencies) 		←	→		
Concomitant treatment	←				→

 Patients using ED treatment (device or medication), a 5-week screening period will be observed (including 1 week washout). Patients not using any form of ED treatment only need to observe a 4-week screening period.

 Assessments at this Visit may be performed via Telehealth. The site will phone the patients to prompt them to complete the IIEF, SEAR, EPIC and climacturia questionnaires, if required in the

protocol schedule of assessments. The completed questionnaires will be brought to the site at the next scheduled on-site visit.

 Eligibility assessment at Visit 2 will consider whether the patient has had the 4 requested sexual intercourse attempts during the screening period and has a score of <= 25 on the IIEF-EF questionnaire at Visit 2.

 IIEF, EPIC, climacturia, and SEAR Baseline scores will be obtained at Visit 2

 At Visit 2, sufficient MED3000 will be dispensed to meet the needs of each patient's entire participation in the study (36 tubes)

 Adverse Events will be recorded from the point that patient and partner sign their respective informed consent forms.

 Visit 5 assessments will be undertaken for patients who withdraw from the treatment period prematurely

 PSA and testosterone samples do not need to be drawn if the patient has had these completed within 4 months of the Visit 1 visit. Samples may also be drawn at a timepoint between Visits 1 and 2 as long as they are available to assess eligibility at Visit 2.

 The female may sign the consent form at a date either prior to or after the patient provides consent. However, both patient and partner must sign their respective consent forms before any study related activity begins such as male lab draws and avoidance of erectogenic aids.

